# **10 CONCOMITANT TREATMENT**

#### Medication(s) or systemic treatments

All concomitant medications shall be recorded on case report forms.

No systemic anti-cancer treatment is permitted concurrently with VK-2019, including complementary, alternative, herbal, or nutritional supplement-based treatments whose purpose is for anti-cancer effect. Supportive agents such as bisphosphonates, denosumab, and RANKL inhibitors are permitted.

## **Concomitant Radiotherapy or Surgery**

Focal treatment with either surgery or radiation for non-target lesions to alleviate discomfort is permitted after discussion with the study sponsor. For non-emergent, elective major surgical procedures, the investigational agent should be held one week before and one week after the procedure. G-tube placement or placement of indwelling catheters are not considered major surgical procedures.

## **Disallowed medications**

In vitro studies have indicated that VK-2019 is a substrate for OATP1B1 and OATP1B3.

Dosing of VK-2019 in combination with OATP1B1 or OATP1B3 substrates or inhibitors are not permitted during the first two cycles of treatment with VK-2019. See Appendix 2 for a list of restricted medications. Use of OATP1B1 or OATP1B3 substrates or inhibitors after Cycle 2 should be done in consultation with the Sponsor.

It is not known how the administration of VK-2019 will affect the absorption of drugs that are transported by OATP1B3, e.g., atorvastatin, and concomitant use of these drugs should be done with caution.

# 11 STUDY PROCEDURES AND OBSERVATIONS

See Tables 1-6 for a complete schedule and descriptions of protocol specified procedures and evaluations.

# Medical and Oncology History

A detailed medical history will be taken at Screening, including significant, relevant medical history within the past 5 years and all cancer related history, including treatment, surgical, and radiation history.

#### Physical Exam

Body systems assessed during physical exams should be performed per institutional practice

#### Lab Assessments

Table 9:	Assessments	by Type	and Visit
----------	-------------	---------	-----------

Lab Type	Assessment	Visits
Hematology	CBC with Differential	All visits (excluding LTFU)
Chemistry	Na, K, Cl, CO2, BUN, Cr,	All visits (excluding LTFU)
	glucose, Ca, total bili, AST, ALT,	
	ALP, albumin, total protein, Mg	
Urinalysis	pH, specific gravity, glucose,	Screening, D1 of each cycle,
	ketones, blood, protein, nitrates,	EOT, and Safety FU
	leukocytes	
Coagulation	PT, PTT, INR	Screening, D1 of each cycle,
		EOT, and Safety FU
Pregnancy	Blood or urine	EU only:
		Screening, D1 of each cycle,
		EOT, and Safety FU
		All other regions:
		Screening and EOT
EBV DNA	EBV DNA in plasma	Screening, C2D0, C2D0, and
		EOT

# Electrocardiograms

ECGs using a 12-lead tracing will be collected in triplicate (i.e. three 10-second tracings approximately 1 minute apart) and should be performed in the supine position unless collecting them in this position is not feasible. A machine with the capacity to calculate standard intervals automatically should be used. At each time point, heart rate and PR, R-R, QRS, and QT intervals will be calculated.

#### **Tumor Assessments**

Response and progression in this study will be evaluated using RECIST 1.1 and its definitions of evaluable lesions, response, measurable disease, target lesions, non-target lesions. Tumor assessments must be performed using computed tomography (CT), positron emission tomography (PET)/CT, or magnetic resonance imaging (MRI). Assessments should include evaluation of the neck, chest, abdomen, and pelvis, however, on a case-by-case basis the investigator and Medical Confidential Page 55 of 81

Monitor may agree to limit scan volume for a given patient (e.g., due to concern over radiation exposure).

The same modality used at baseline should be used throughout the study.

# Follow-Up

# 11.6.1 Safety Follow-Up

A safety follow-up visit will be conducted at least 28 days ( $\pm$  7 days) after the patient's last dose of study drug.

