#### Protocol VK-2019-001

#### Version 9.0, 15-October-2019

### Table 1: Schedule of Events in Phase 1 Dose Escalation

Assessment 	Screening	Сус	le 1	Cycle 2		Cycle 3 and Odd Cycles 	Cycle 4 and Even Cycles 	ЕОТ	Safety FU	LTFU
	Within 28 days of C1D0	Day 0	Day 14 (± 1 d)	Day 0 (+3 d)	Day 14 (± 3 d)	Day 0 (± 3 d)	Day 0 (± 3 d)	7 d $(\pm 3 d)$	$28 d (\pm 7 d)$	q12 w $(\pm 1 w)$ post-last dose
Informed consent	X		$(\pm 1 \text{ u})$	(+5 u)	(± 5 u)	(± 5 u)	(= 5 u)	post lust dose	post lust dose	post lust dobe
Medical/Oncology History	Х									
ECOG Performance Status 	X	$X^{10}$						Х		
Vital Signs 	Х	Х	Х	Х	Х	X	Х	Х	Х	
Height & Weight 	Х	$X^{10}$		$X^{10}$		$X^{10}$	X 	Х	Х	
Physical Examination 	X	$X^{10}$		$X^{10}$		X 	X 	Х	Х	
Hematology Labs 	Х	$X^{10}$	Х	$\mathrm{X}^{10}$	Х	$\mathrm{X}^{10}$	$\mathrm{X}^{10}$	Х	Х	
Chemistry Labs 	X	$X^{10}$	Х	$X^{10}$	Х	$X^{10}$	$X^{10}$	Х	Х	
Urinalysis 	X	X 		$X^{10}$		$X^{10}$	$X^{10}$	Х	Х	
Coagulation Panel 	Х	$X^{10}$		$X^{10}$		$X^{10}$	$X^{10}$	Х	Х	
Pregnancy Test 	X	X 		$X^{6,10}$		X 	$X^{6,10}$	Х	$X^{6,10}$	
Triplicate ECG 	X	Х	Х	Х				Х	Х	
Adverse Events	Х	Х	Х	Х	Х	Х	Х	Х	Х	
Concomitant Medications	Х	Х	Х	Х	Х	Х	Х	Х	Х	
VK-2019 	X									
PK Plasma 		Х	Х	Х		X (C3 only)				
Plasma EBV DNA 	X		Х	Х	Х	X (C3 only)		Х		
Tumor Assessments 	X					X 		X 		X 
Survival										$X^{14}$

Protocol VK-2019-001

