## 11.6.2 Long-Term Follow-Up

All patients that discontinue study treatment will be followed for:

- Survival: Via clinic visit (either at the study site or outside facility), telephone, or videotelephony until a) death, b) withdrawal of consent, c) they are lost to follow-up, d) the Sponsor notifies sites that survival follow-up is no longer required, or e) termination of study by the Sponsor, and
- Assessment of treatment-related SAEs until resolution to baseline or Grade  $\leq 1$ .

Patients discontinuing treatment due to reasons other than radiographic disease progression will have their tumor assessed (using the same modality that was used during study treatment) every 12 weeks ( $\pm$  14 days) for up to 2 years after the last treatment visit, or until a) they have progressive disease, b) they start a new therapy for their cancer, b) death, c) withdrawal of consent, d) they are lost to follow-up, e) the Sponsor notifies sites that tumor assessment is no longer required during long-term follow-up, or f) termination of study by the Sponsor.

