## **Reporting Period**

For AEs (including SAEs), the active reporting period to the sponsor or its designated representative begins from the time the patient provides informed consent, which is obtained prior to the patient's participation in the study, i.e., prior to undergoing any study-related procedure and/or receiving investigational product, until either a) 28 calendar days after the last administration of the investigational product, or b) initiation of a new anti-cancer therapy. Should an investigator be made aware of any SAE considered at least possibly related to study drug occurring any time after the active reporting period, it must be promptly reported. Confidential Worsening of signs and symptoms of the malignancy under study should be reported as AEs in the appropriate section of the CRF. Disease progression assessed by measurement of malignant lesions on radiographs or other methods should not be reported as adverse events.

An adverse reaction is defined as any AE caused by the use of a drug. Adverse reactions are a subset of all suspected adverse reactions, for which there is reason to conclude that the drug caused the event. Examples of adverse reactions include but are not limited to:

- Abnormal test findings;
- Clinically significant symptoms and signs;
- Changes in physical examination findings;
- Hypersensitivity;
- Drug abuse;
- Drug dependency.

Additionally, they may include the signs or symptoms resulting from:

- Drug overdose;
- Drug withdrawal;
- Drug misuse;
- Drug interactions;
- Exposure during pregnancy;
- Exposure via breastfeeding;
- Medication error.

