6.1.1 Safety Follow-Up

A safety follow up visit will be conducted at least 28 days (\pm 7 days) after the patient's last dose of study drug.

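### The Safety FU window (28 ± 7 days) contradicts its own 28-day minimum and lets the last scheduled AE assessment fall up to 7 days before AE reporting closes

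*Protocol*

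**What the plan says.** Days below are counted from the last dose unless stated otherwise.

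- **Visit timing, text.** Protocol 11.6.1: "A safety follow-up visit will be conducted at least 28 days", followed by ± 7 days. SAP 6.1.1 has the same rule: "A safety follow up visit will be conducted at least 28 days", again with ± 7 days.
- **Visit timing, schedules.** The Safety FU columns of Tables 1, 2 and 3 give 28 days ± 7 after the last dose, with no minimum.
- **Reporting period.** Protocol 13.3 keeps active AE and SAE reporting open "until either a) 28 calendar days after the last administration of the investigational product, or b) initiation of a new anti-cancer therapy".
- **Last scheduled AE check.** In all three tables the "Adverse Events" row is marked up to Safety FU and is blank under long-term follow-up. Concomitant medications, laboratory tests, vital signs and ECGs stop at the same visit.
- **What follows.** Section 11.6.2 provides for survival status, tumor assessments in patients who stopped without radiographic progression, and "Assessment of treatment-related SAEs until resolution to baseline" or Grade 1 or lower.
- **Safety net.** Section 13.3 adds a passive rule for the time after the period closes, which begins "Should an investigator be made aware of any SAE considered at least possibly related to study drug". It covers related SAEs only.

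**The concern.** The visit that collects late AEs should fall on or after the day on which AE collection ends. Here nearly half of the permitted visit days come before it. Sites usually book visits from the schedule tables, so a Day 21 visit would be made in good faith and would not be a deviation.

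AEs are the Phase 1 primary endpoint (Protocol 14.1.1, SAP 4.1). Neither TEAE definition (Protocol 14.5.1, SAP 7.14.1) has an end date, so the collection window decides what is counted. If that window varies with the visit date, ascertainment after treatment differs between patients, and the error can only be an undercount.

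**Working it through.** The plan gives no figure to reproduce. The check is date arithmetic plus a reading of the schedules.

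**Inputs.** Visit target 28 days, tolerance ± 7 (Tables 1-3, Protocol 11.6.1, SAP 6.1.1). Reporting closes on Day 28 or at the start of new anti-cancer therapy (Protocol 13.3), which I read as whichever comes first. Long-term follow-up is every 12 weeks ± 1 week (Tables 1-3).

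**1. Permitted visit days.** 28 − 7 = Day 21 to 28 + 7 = Day 35, which is 15 days.

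**2. Reporting days after the last scheduled AE assessment.** Uncovered days = max(0, 28 − visit day), for a patient who has not started new therapy:

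| Visit day | Uncovered days |
|---|---|
| 21 | 7 |
| 22 | 6 |
| 23 | 5 |
| 24 | 4 |
| 25 | 3 |
| 26 | 2 |
| 27 | 1 |
| 28-35 | 0 |

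Seven of the 15 permitted days leave a gap and eight leave none. The worst case is 7/28 = 25% of the post-treatment period, for a visit on exactly Day 21. The documents give no distribution of visit days. If visits were spread evenly over the window (an assumption), the mean gap would be (7+6+5+4+3+2+1)/15 = 28/15 = 1.9 days, or 1.9/28 = 6.7% of the period.

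**3. The alternative reading.** If the 28-day minimum governs, visits fall on Days 28-35 and the gap is 0. The minus side of the tolerance, printed in all five places, then has no meaning.

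**4. Does a later contact close the gap?** The next scheduled contact is at 12 × 7 = 84 days, ± 7, so Days 77-91. (Scans may fall within ± 14 days.) It has no AE item beyond treatment-related SAEs, and survival may be checked by telephone.

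**5. Are DLTs affected?** A patient evaluable by dose count takes at least 75% × 28 = 21 doses in Cycle 1. Counting from Cycle 1 Day 0, the last dose is no earlier than Day 20, so the earliest Safety FU visit is 20 + 21 = Day 41, after the 28-day DLT window. A patient evaluable because of a DLT has already been counted.

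**6. Is the Simon design affected?** No. It uses tumor response, not AEs.

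**The case against.** The strongest reply is that only scheduled questioning is cut short. Reporting is not. Section 13.3 holds the period open to 28 calendar days whatever the visit date. Section 13 makes observed and volunteered AEs reportable regardless of causality, and SAEs must reach the sponsor within 24 hours of site awareness. This stands, and it limits the point considerably.

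A reader might infer more: that a quarter of post-treatment AE data is lost, or that deaths, AE durations and dose decisions are compromised. The documents do not support that.

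- Deaths come to light through survival follow-up, and a fatal event within the period is an SAE.
- AEs already known at the visit are followed until resolved, so their duration is still captured.
- Related SAEs have two further safeguards, in 11.6.2 and 13.3.
- The AE tables that SAP 7.14.1 singles out are TEAEs leading to treatment discontinuation or death, and first-cycle DLTs. An AE starting three to four weeks after the last dose would not ordinarily be a reason for stopping.
- The 25% is the worst case for a single patient, and the gap closes once new anti-cancer therapy starts.

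One can also say that the 28-day minimum, taken literally, already settles the matter. It does so only by disregarding the tolerance in the same sentence and in three tables. Finally, editing the SAP alone changes no data collection, because SAP 6.1.1 only restates the protocol. That is correct; the SAP edit is for consistency.

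**Conclusion.** The point holds as an internal contradiction with a small, one-directional effect. Protocol 11.6.1 and SAP 6.1.1 cannot be followed as written, and Tables 1-3 permit a final AE assessment 1 to 7 days before the reporting period ends (at most 7 of 28 days). The exposed events are mainly new-onset non-serious AEs and non-fatal unrelated SAEs, starting between the visit and Day 28, that never reach the site by another route. General AE incidence and listings could miss a few of these. The documents do not show how many patients would be seen before Day 28 or how many such events to expect, so the undercount cannot be put as a number of events.

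This rests on sites using the tables as printed and on the patient not having started new anti-cancer therapy. MTD and Simon decisions are not shown to be affected. The one theoretical route into DLTs is the SRC's discretion to declare a DLT outside the usual timing.

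**What to change.** Reconcile the Safety FU column of Tables 1, 2 and 3, Protocol 11.6.1 and SAP 6.1.1 with Protocol 13.3, so that the last scheduled AE assessment does not precede the end of the reporting period. One way is a window of 28 days (+7), that is Days 28-35. This keeps the 28-day minimum already written and drops only the minus side. State that an earlier visit is acceptable when new anti-cancer therapy is about to start, since reporting ends then anyway.

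The cost is an edit to three table headers and two sentences, with no extra visit and slightly less scheduling flexibility.

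The SAP serves an abbreviated CSR and already states that no biopsies were collected, so data collection may be well advanced. If the visits have taken place, leave the data as they are and report how many patients had their last AE assessment before Day 28, apart from those who had already started new therapy.

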## 11.6.2 Long-Term Follow-Up

All patients that discontinue study treatment will be followed for:

- Survival: Via clinic visit (either at the study site or outside facility), telephone, or videotelephony until a) death, b) withdrawal of consent, c) they are lost to follow-up, d) the Sponsor notifies sites that survival follow-up is no longer required, or e) termination of study by the Sponsor, and
- Assessment of treatment-related SAEs until resolution to baseline or Grade  $\leq 1$ .

Patients discontinuing treatment due to reasons other than radiographic disease progression will have their tumor assessed (using the same modality that was used during study treatment) every 12 weeks ( $\pm$  14 days) for up to 2 years after the last treatment visit, or until a) they have progressive disease, b) they start a new therapy for their cancer, b) death, c) withdrawal of consent, d) they are lost to follow-up, e) the Sponsor notifies sites that tumor assessment is no longer required during long-term follow-up, or f) termination of study by the Sponsor.

# **12 PHARMACOKINETICS AND PHARMACODYNAMICS**

#### PK and Metabolite Profiling Assessments

Specific visits and timepoints for each PK blood and urine collection are specified in Tables 3-6. See the lab manual for PK collection, processing, and shipping instructions. The PK assessments during Cycle 1 may be repeated if the PK sampling is missed for any reason or if the PK data collected are deemed non-evaluable.

Timing of sampling may be modified administratively based upon emerging PK data, but the number of samples will not increase.

PK samples used for the determination of VK-2019 concentrations and its metabolites will be analyzed by a central laboratory on behalf of the Sponsor, using an appropriate bioanalytical method. Full details of the analytical method used will be described in a separate bioanalytical report.

PK samples may be subjected to additional analyses by the Sponsor in order to further investigate the presence and/or identity of additional drug metabolites.

12.1.1 CSF for Analysis of VK-2019

If a patient undergoes a lumbar puncture while on trial as part of standard of care medical evaluation (i.e., not required per protocol), if possible, an additional sample of CSF should be collected for exploratory analysis of VK-2019 concentrations. If feasible, an unscheduled plasma PK sample should also be collected at approximately the same time. See the lab manual for CSF collection, processing, and shipping instructions.

## Effect of EBNA1 Inhibitor VK-2019 on Plasma EBV DNA

Specific visits and timepoints for each plasma EBV DNA collection are specified in Tables 4-6. Plasma EBV DNA sample analysis will be performed by each participating institution's clinical lab.

Analysis of plasma EBV DNA will explore whether VK-2019 has any impact of NPC EBV DNA shedding into the bloodstream at time points prior to the standard of practice clinical and imaging analyses for tumor response.(24) It is possible that early changes in plasma EBV DNA in this setting may provide early hints of activity in an individual patient relative to conventional tumor response evaluations. It is also possible that early plasma EBV DNA alterations in initial cohorts of patients may reveal evidence of an impact of VK-2019 at lower dose levels than the usual clinical parameters used for evaluation of anti-cancer effect and therefore may provide evidence as a biomarker for activity in an accelerated time frame. (25) A harmonized assay for plasma EBV DNA testing will be utilized in this study and analysis will be performed at a central lab on behalf of the Sponsor.

## Intra-Tumor EBNA1 Activity Inhibition by VK-2019

During the Phase 2a Dose Expansion, patients may elect to provide biopsies for EBNA1 activity alteration associated with VK-2019 administration. Using biopsied material before and after treatment from selected patients, DNA will be isolated and quantitative PCR (qPCR) performed on collected tissue. Using validated EBV specific primers, GAPDH control primers, and the Namalwa cell line (which has 2 EBV copies/cell), EBV genome copy number will be assessed on per cell basis. In addition, RNA will be isolated from biopsied material and Nanostring gene expression analysis of viral and cellular genes will be performed. The PanCancer Pathways panel will be used, Confidential Cullinan Apollo Corp Protocol VK-2019-001

supplemented with 30 EBV viral genes to assess which pathways are affected by EBNA1 inhibition. These studies will help to establish proof-of-mechanism of EBNA1 inhibitors for the treatment of EBV-positive NPC.

Biopsy samples may be subjected to additional analyses by the Sponsor in order to further investigate the presence and/or identity of additional biomarkers and/or mechanisms of activity.

# **13** ADVERSE EVENTS AND SERIOUS ADVERSE EVENTS

## Definitions of an AE

An AE (also known as an adverse experience) is defined as any untoward medical occurrence associated with the use of a drug in humans, whether or not considered drug related. More specifically, an AE can be any unfavorable and unintended sign (e.g., an abnormal laboratory finding), symptom, or disease temporally associated with the use of a drug, without any judgment about causality. Laboratory values that the investigator determines to be not clinically significant should not be considered as AE. Additionally, an adverse event can arise from any use of the drug (e.g., off-label use, use in combination with another drug) and from any route of administration, formulation, or dose, including an overdose.

For all AEs, the investigator must pursue and obtain information adequate both to determine the outcome of the AE and to assess whether it meets the criteria for classification as an SAE requiring immediate notification to the sponsor or its designated representative. For all AEs, sufficient information should be obtained by the investigator to determine the causality of the AE. The investigator is required to assess causality. Follow-up by the investigator may be required until the event or its sequelae resolve or stabilize at a level acceptable to the investigator and the sponsor concurs with that assessment.

Any AE assessed by the investigator and/or Sponsor to be serious will be reported by the sponsor as an SAE. To assist in the determination of case seriousness further information may be requested from the investigator to provide clarity and understanding of the event in the context of the clinical trial.

# AE Reporting

[figure not shown]
All observed or volunteered adverse events regardless of suspected causal relationship to the investigational product will be reported as described in the following sections. For each mandated AE evaluation, there may be an AE query form developed to actively query patients and to document high priority AEs for collection, based upon preclinical AE data and emerging AE data as the study continues.

All documentation of AEs should include the following elements, further discussed below:

- AE term using the CTCAE v5.0
- AE severity grading using the CTCAE v5.0
- AE seriousness per the below guidance
- AE attribution (causality) per the below guidance
- AE expectedness for all AEs attributed to the investigational agent

## **Reporting Period**

For AEs (including SAEs), the active reporting period to the sponsor or its designated representative begins from the time the patient provides informed consent, which is obtained prior to the patient's participation in the study, i.e., prior to undergoing any study-related procedure and/or receiving investigational product, until either a) 28 calendar days after the last administration of the investigational product, or b) initiation of a new anti-cancer therapy. Should an investigator be made aware of any SAE considered at least possibly related to study drug occurring any time after the active reporting period, it must be promptly reported. Confidential Worsening of signs and symptoms of the malignancy under study should be reported as AEs in the appropriate section of the CRF. Disease progression assessed by measurement of malignant lesions on radiographs or other methods should not be reported as adverse events.

An adverse reaction is defined as any AE caused by the use of a drug. Adverse reactions are a subset of all suspected adverse reactions, for which there is reason to conclude that the drug caused the event. Examples of adverse reactions include but are not limited to:

- Abnormal test findings;
- Clinically significant symptoms and signs;
- Changes in physical examination findings;
- Hypersensitivity;
- Drug abuse;
- Drug dependency.

Additionally, they may include the signs or symptoms resulting from:

- Drug overdose;
- Drug withdrawal;
- Drug misuse;
- Drug interactions;
- Exposure during pregnancy;
- Exposure via breastfeeding;
- Medication error.

